12.6.2 Kidney Stone Events

Frequency of kidney stone events after 12 and 24 months of treatment. Kidney stone events are defined as:

- Subject- or investigator-reported symptoms, or
- Stone passages or removals, or
- Increase in the number of kidney stones as assessed by ultrasound

Kidney stone events after 12 and 24 months of open-label Oxabact treatment will be summarised using descriptive statistics. Incidence rates of kidney stone events (defined as the number of events divided by the total person-years) will be calculated along with the number of subjects with a stone event. Risk ratio and risk difference between the two treatment groups will be presented in combination with a 95% CI.

Time lost at work or school due to kidney stone events will be summarised.

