6.2 Key secondary endpoint(s)

The secondary endpoints are the following:

- Change from baseline in total plasma oxalate concentration after 12 and 24 months of open-label Oxabact treatment.
- Frequency of kidney stone events after 12 and 24 months of open-label Oxabact treatment. Stone events are defined as:
 - Patient- or investigator reported symptoms, or
 - Stone passages or removals, or
 - Increase in number of stones assessed by ultrasound.

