7.6.2 Key secondary endpoints

The key secondary endpoints will be presented using the FAS population, and all individual data will be listed as well.

Total plasma oxalate

The key secondary endpoint change from baseline in total plasma oxalate concentration, will be analysed using a similar analysis (descriptive plus supportive MRMM including the slopes) as proposed for the primary endpoint (see section 7.6.1), and no additional sensitivity analyses will be performed. Similar descriptive statistics per visit (absolute and change from baseline) and plots will be created.

Additionally, a combined plot for total plasma oxalate concentration and eGFR over time will be created using a double-axis display – this plot will be created for each subject, and a summary plot presenting mean +/- SE values per treatment group and overall will be made.

Summary statistics will also be created for the observed minimum and maximum total plasma oxalate concentration values during ePHex-OLE, as well as its changes from baseline using both baselines. Also, plots will be created to present the shift from baseline to the minimum or maximum value, combined for all subjects per treatment group and overall.

In addition, a frequency tabulation will be created based on the number of subjects achieving ‘near-normalization’ of total plasma oxalate concentration (<10 µmol/L) at least twice during 12 months and during 24 months of open-label treatment. This table will also include the response assessments for < 10 µmol/L during 12 months and during 24 months of open-label treatment.

Furthermore, percent change from baseline in total plasma oxalate concentration after 12 and 24 months of treatment will be displayed descriptively per treatment and overall, using both baselines.

Kidney stone events

Kidney stone events are defined as subject- or investigator reported symptoms (as in the CRF AE or PH medical history pages), or number of stones assessed by Ultrasound (US). As a consequence, three summary tables on stone events will be presented, as follows:

- Stone events during treatment, based on AE
- Stone events during treatment, based on US

Here, during treatment is defined as first to last dose date of ePHex-OLE. Where applicable, stones left and right will be combined into one overall kidney stone number for summary tables and analysis.

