Descriptive statistics of the occurrence of kidney stones and the number of subjects with a stone event after 12 and 24 months of open label treatment will be presented per treatment group and overall, separately as based on AE and based on US datasets.

Descriptive statistics on stone events using the AE dataset will include a summary of days missed at school/work due to a stone event and other relevant data related to stone events.

Incidence rate of kidney stones is the rate at which kidney stone events occur in the population, and defined as the number of kidney stone cases per subject-year(s). The calculation of the incidence rate is the number of kidney stone occurrences during the study time period divided by the group of subjects susceptible to a stone event (i.e. the FAS), expressed as person-time and

calculated as sum of the treatment duration time of all subjects in the FAS. This calculation is accomplished as follows:

- Denominator: $\sum t_i$, where t_i = treatment duration of subject i in years (total # days divided by 365.25), where treatment duration is determined based on first and last dose date.
- Numerator: the total number of kidney stone occurrences during treatment (first to last dose date)
- Incidence rate=numerator/denominator

Since this analysis is done both after 12 months and after 24 months of treatment, in case of 12 months the date of visit 6 is used instead of last dose date.

The use of this measure implies the assumption that the incidence rate is constant of different periods of time. The incidence rates will be presented per treatment group. As these incidence rates are determined per treatment group, comparisons can be done using descriptive statistics of incidence rate difference (IRD) and incidence rate ratios (IRR). IRD and IRR are defined as follows, assuming the following exposure table:

			Treatment exposure	
			O - O	P - O
Outcome	12 months	Occurrences	a	B
		Person-time	PT1	PT2
	24 months	Occurrences	a	b
		Person-time	PT1	PT2

Then $IRD=(a/PT1) - (b/PT2)$ and $IRR=(a/PT1)/(b/PT2)$ is calculated for 12 months and 24 months. These will be presented in combination with a 95% CI.

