7.6.4 Subgroup analyses

Subgroup analyses using descriptive statistics of the following endpoints may be presented if considered feasible: change from baseline for eGFR, change from baseline for total and free plasma oxalate concentration, change from baseline for 24h urine oxalate excretion (non-centrifuged only), stone events incidence rate (as per adjudicated data) and change from baseline for speckle tracking and traditional echocardiography (limited to LVEF/GLS). Presentations will be done for each visit. Both baselines will be used. The analyses will be based on the following subgroups, provided the subgroups are sufficiently large (>2):

- Subjects with a baseline urinary oxalate excretion (non-centrifuged) above and equal to or below 1.87 mmol/L/24h/1.73 m² respectively (mean of the two values during screening/baseline of the ePHex study).
- Subjects above or equal to and below 18 years of age at baseline of the ePHex study.
- Subjects with a baseline eGFR above or equal to (\geq) and below ($<$) 60 ml/min/1.73m² respectively (mean of the obtained values during screening/baseline of the ePHex study calculated by the Schwartz/CKiD equation⁴), with correction for 18-23 years.
- Race.
- Gender.
- Progressors and non-progressors (see section 11.1) based on historical eGFR (i.e. eGFR prior to treatment start including the baseline/screening values of the ePHex study), using the Schwartz/CKiD equation.

⁴ The Schwartz CKiD 2009 creatinine-based “bedside Schwartz” equation for children (below 18 years of age) and 2009 creatinine-based CKD-EPI equation for adults.

For the subgroup analyses only the FAS population will be used. No formal testing of subgroups will be performed due to small sample sizes. No plots will be created.

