14.2.16	Summary statistics for minimum and maximum total plasma oxalate values, including change from baseline. (FAS). Two baselines.
14.2.17	Total plasma oxalate concentration (unit) percent change from baseline over time (FAS). Two baselines.

14.2.18	Frequency tabulation on subjects with 'near-normal' total plasma oxalate levels (FAS). Two baselines.
14.2.19	Mixed Repeated Measures Model result total plasma oxalate. (FAS)
14.2.20	LS estimates total plasma oxalate. (FAS)
14.2.21	Slope results total plasma oxalate. (FAS).
14.2.22	Mean (+/-SE) total plasma oxalate versus time plot, per treatment (FAS). Similar plot for change from baseline.
14.2.23	Individual total plasma oxalate versus time plot (FAS). Similar plot for change from baseline.
14.2.24	Shift plots from baseline to minimum/maximum value for total plasma oxalate. (FAS).
14.2.25	Spaghetti plots per treatment group of the actual total plasma oxalate concentration values (FAS).
14.2.26	LS mean +/- SE plot total plasma oxalate (FAS)
14.2.27	Mean (+/- SE) plots eGFR/total plasma oxalate versus time using double axes (FAS) - Two calculation methods (2009 and 2012 formulae).
14.2.28	Mean (+/- SE) plots eGFR/total plasma oxalate versus time using double axes (FAS) - Two calculation methods (2009 and 2012 formulae).
14.2.29	Descriptive statistics kidney stone events (FAS), based on AE and US, respectively
14.2.30	Incidence rate of kidney stone events (FAS), based on AE and US, respectively
14.2.31	Descriptive statistics stone frequency by subgroup (FAS)
14.2.32	Descriptive statistics US data (FAS)
14.2.33	Statistical analysis stone frequency, based on AE and US, respectively
14.2.34	Descriptive statistics STE parameters (FAS) – raw and cfb
14.2.35	Descriptive statistics traditional echocardiography parameters (FAS) – raw and cfb
14.2.36	Descriptive statistics main STE/TE parameters (LVEF/GLS) by subgroup (FAS) – raw and cfb
14.2.37	Mean (+/-SE) main STE/TE parameters (LVEF/GLS) versus time plot, per treatment (FAS)
14.2.38	Individual main STE/TE parameters (LVEF/GLS) versus time plot, per treatment (FAS)

14.2.39	Descriptive statistics free plasma oxalate (FAS) – raw and cfb
14.2.40	Descriptive statistics free plasma oxalate by subgroup (FAS) – raw and cfb
14.2.41	Mean (+/-SE) free plasma oxalate versus time plot, per treatment (FAS). Similar plot for change from baseline.
14.2.42	Individual free plasma oxalate versus time plot (FAS). Similar plot for change from baseline.

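### SAP 7.6.2 does not analyse the stone endpoint that the protocol and SAP 6.2 define: its working definition differs, and no planned output combines the components

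*SAP*

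**What the plan says.** Protocol 10 and 12.6.2, with SAP 6.2, define a stone event by three components joined by the word or. The first is reported symptoms. The second reads "Stone passages or removals, or" in SAP 6.2, and the protocol wording is the same. The third, in Protocol 12.6.2, is "Increase in the number of kidney stones as assessed by ultrasound". Protocol 10.2 gives the same three parts in more detail.

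SAP 7.6.2 restates the definition before describing the analysis: "subject- or investigator reported symptoms (as in the CRF AE or PH medical history pages), or number of stones assessed by Ultrasound". It continues "As a consequence, three summary tables on stone events will be presented, as follows" and lists two tables, one from AE records and one from ultrasound (US). Descriptive statistics at 12 and 24 months are to be given "separately as based on AE and based on US datasets".

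The table list in SAP 12.3 follows the same split. Table 14.2.30 is "Incidence rate of kidney stone events (FAS), based on AE and US, respectively" and Table 14.2.33 is "Statistical analysis stone frequency, based on AE and US, respectively". For subgroups, SAP 7.6.4 names "stone events incidence rate (as per adjudicated data" as the quantity to report. SAP 8, which lists changes from the protocol, has no entry on stones.

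**The concern.** The endpoint is a composite: a subject or an occasion counts if any component is met. The analysis section uses another definition and reports two sources side by side without joining them. Three things are at stake.

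- **The reported quantity.** An AE-based rate and an ultrasound-based rate are each informative, but neither is the frequency of the defined event. They cannot simply be added, because one stone may appear in both.
- **The ultrasound component.** A count of stones is not a count of new stones. Many of these patients may carry stones at Month 0.
- **Freedom after the data are seen.** With no rule for combining the sources, the choice between the AE result, the ultrasound result or some union could be made at reporting. Protocol 4.4.1.4 already warns, for the earlier extension study, that a new stone event is hard to define in this population.

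**Working it through.** No sample size, power or expected rate is given for stone events, so the check is a side-by-side reading with simple counts.

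**Step 1: the definition.**

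| Component | Protocol 10, 10.2, 12.6.2 and SAP 6.2 | SAP 7.6.2 |
|---|---|---|
| Reported symptoms | included | included, from the AE or PH medical history pages |
| Passing or removal of a stone | included | not named |
| Ultrasound | a rise in the number of stones | the number of stones |

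The source definition has 3 components. The working definition has 2, and one of those 2 is altered.

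**Step 2: the number of tables.** SAP 7.6.2 announces 3 and lists 2, so 3 − 2 = 1 is missing. The text does not say what it was meant to be.

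**Step 3: the planned outputs (SAP 12.3).**

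- 14.2.29, descriptive statistics: split by AE and US.
- 14.2.30, incidence rate: split by AE and US.
- 14.2.33, count model: split by AE and US. SAP 7.6.2 speaks of a total number of events for this model, but its table is split.
- 14.2.31, subgroups: no source named in the title; SAP 7.6.4 points to adjudicated data.

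Outputs stated to combine AE and ultrasound events: 0 of 4.

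**Step 4: can the composite be recovered from the split tables?** Let A be the count from AE records, U the count of ultrasound rises and C the composite, with each AE event matched to at most one ultrasound rise. Then

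max(A, U) ≤ C ≤ A + U.

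The width of this interval is A + U − max(A, U) = min(A, U), the smaller of the two counts. For numbers of subjects the same bounds hold, with the upper end capped at the group size. The tables do not show the overlap, so they cannot narrow the interval.

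**Step 5: rise against number.** Take a hypothetical subject with 5 stones on every scan and no symptoms, passages or removals. Under the protocol the ultrasound component gives 5 − 5 = 0 events at Month 12 and 5 − 5 = 0 at Month 24. SAP 7.6.2 adds left and right stones into one number and uses total stone occurrences as the rate numerator. Read literally, this subject could contribute 5 stones at a scan. The SAP does not say that unchanged stones are excluded.

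**Step 6: adjudication.** SAP 7.6.4 is the only place in the supplied text that mentions it. Protocol 10.2 leaves it to the investigator to decide whether events close in time are separate. Protocol 10.6.2 provides blinded central reading, but of ultrasound images only. SAP 10 lists the incoming data files and names none for adjudicated stone events.

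**The case against.** Several stronger readings are tempting, and the documents do not support them.

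*A reader might infer that passages and removals are lost.* Protocol 6.3.2 and 10.2 send stone event information to the AE eCRF, Protocol 10.2 counts passages and removal procedures as stone events, and SAP 7.7.1 confirms that stone events are on the AE pages. SAP 6.2 also keeps the component. Such events may well reach the AE-based table. What stands is a contradiction between SAP 6.2 and 7.6.2, not a shown loss of data.

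*A reader might infer that the endpoint has no result.* That goes too far. Counts, subjects with events, rates, rate ratios and rate differences are planned for each source at 12 and 24 months. AE records and ultrasound data are listed by subject (Listings 16.2.7.1 and 16.2.6.3). With the 18 subjects stated in SAP 2.4, someone could count by hand those with either kind of event. That is still not a planned, defined output.

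*A reader might infer that the trial has no adjudicated data.* The supplied text only fails to describe any. Addendum 1 and the ePHex SAP are cited but not supplied, and the subgroup summaries are optional.

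*A reader might size the gap from the earlier extension study,* where 31.3% and 65.0% of subjects had a stone event (Protocol 4.4.1.4). Those figures already mix stones with signs and symptoms, concern an older product, and are called into question by the protocol itself. Any range built on them would only repeat the ultrasound share that one chose to assume.

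*A reader might infer that the missing third table is the composite.* It may equally be a remnant of a medical history table, since SAP 7.6.2 mentions those pages while SAP 7.1 says historical ePHex data will not be presented again.

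It is also fair that everything here is descriptive, and that matching an AE to an ultrasound rise over about 12 months between scans needs judgement.

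**Conclusion.** The point stands as a mismatch between the defined endpoint and its analysis. Followed as written, SAP 7.6.2 reports two source-specific quantities, uses an ultrasound measure that could include stones already present at baseline, and gives no composite frequency. The table count is wrong by one, the adjudication reference has no described source, and SAP 8 is silent.

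The documents give no basis for a numerical effect. The composite count is undetermined over an interval as wide as the smaller of the two source counts. Neither the primary endpoint nor any error rate is affected, because no formal testing is planned. This should be fixed before database lock, but it does not threaten the trial.

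The conclusion assumes that the outputs are programmed as SAP 7.6.2 and 12.3 describe, and that the addenda not supplied do not already define the composite.

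**What to change.** 1. In SAP 7.6.2, restore the three-component definition of SAP 6.2. State that AE-page stone records include passages and removals. Count an ultrasound event only when the stone number rises from the previous scan (Months 0, 12 and 24).
2. Add a composite output: the number and share of subjects with any component by 12 months and by 24 months, per group and overall. A subject counts once, so no overlap rule is needed. For the composite event rate, rate ratio and rate difference, either fix a simple overlap rule before database lock or show the rate with and without ultrasound-only rises.
3. Keep the AE and ultrasound tables as component tables, and correct the number of tables announced.
4. In SAP 7.6.4, replace the reference to adjudicated data with the composite, or cite the document that describes the adjudication.
5. List any remaining departure from the protocol in SAP 8. One is the move from the risk ratio and risk difference of Protocol 12.6.2 to the incidence rate ratio and difference of SAP 7.6.2.

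The cost is SAP wording, one derived variable and one more table, from data already collected. The overlap rule for rates needs some thought, because the documents show no field linking an AE record to a scan finding. Showing the rate both ways avoids that difficulty.

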During the study period, subjects will have visits every two to three months, i.e., at months 2, 4, 6, 8, 10, 12, 15, 18, 21 and 24. During these visits, plasma oxalate and safety labs will be taken. Subjects will be asked to provide stool samples four times (months 6, 12, 18 and 24) and 24-hour urine five times (months 4, 8, 12, 18 and 24). In addition, subjects will provide a post-treatment follow-up stool sample 4 weeks after intake of last dose of study drug. Echocardiography (STE and traditional) will be assessed four times (months 6, 12, 18 and 24). Ultrasound of the kidney will be done two times (months 12 and 24). Quality of Life will be evaluated by a questionnaire during months

6, 12, 18 and 24 (Table 5). Information on kidney stone events and related symptoms will be captured throughout the study.

Adverse events and concomitant medication will be monitored throughout the study.

Safety evaluation will include physical examination, vital signs and safety labs. Monitoring of AEs, concomitant medication and compliance with the administration of study drug will be performed at each visit. In addition, there will be a 4-week safety follow-up after intake of the last dose of study drug. Furthermore, questions on kidney stone events and related symptoms will also be asked throughout the study.

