10.2 Kidney Stone Events

Kidney stones are hard deposits made of minerals and salts that form inside the kidneys. Most kidney stones (approximately 80%) are calcium stones, usually in the form of calcium oxalate. Stones can also be composed of struvite, uric acid or cystine. Stones vary in size and shape, ranging from a few mms up to 40 mms. Patients can typically pass the smaller stones in the urine. However, larger stones (e.g. >10mm) may require lithotripsy and surgical or endoscopic removal. A kidney stone may not cause symptoms until it moves around within the kidney, passes into the ureter, bladder, or urethra.

Stone Events

In this study, kidney stone events are defined as follows:

- A stone event could be defined as the occurrence of one of the following symptoms due to a kidney stone that may or may not require medical intervention:
 - Abdominal, flank or groin pain, sometimes associated with nausea and vomiting.
 - o Macroscopic hematuria (visible blood in the urine).
 - Urinary tract infection (cloudy or foul-smelling urine, more frequent and/or painful urination than normal, persistent need to urinate and/or urinating small amounts).
- Stone events may also be defined by subject-reported stone passage or by medical procedures to remove identified kidney stones (e.g. lithotripsy, endoscopy, surgery).
- An increase in number of kidney stones as seen in a kidney ultrasound would also be classified as a stone event.

Duration between stone events: if symptoms of a stone event occur simultaneously or close in time to another kidney stone event, the investigator can decide whether or not this should be reported as a separate stone event.

Assements of kidney stone events will be collected by ultrasound (renal imaging) (see section 10.6.2 below) as well as subject-reported stone events or symptoms of events (see definition above). Historical kidney stone events and related symptoms for the past three years preceding study entry will be asked at baseline of the ePHex study. During the study period of the ePHex-OLE study, information will be collected concerning occurrence of self-reported kidney stone event and related symptoms. This information will be captured by completing the applicable items on the Adverse Event eCRF. (Please note this is a data entry convention only and does not replace the per protocol definition of an Adverse Event as defined in Section 11.1).

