2.5 Study flow chart

	Treatment (24 Months)											Post-treatment follow-up (4 weeks) ^{8,9}
Month	0 ¹	2	4	6	8	10	12	15	18	21	24	
Day (+/- 7 days)	0	61	122	183	243	304	365	456	547	638	730	
Visit Number ²	0	1	2	3	4	5	6	7	8	9	10	NA
Clinic Visit	X	X	X	X	X	X	X	X	X	X	X	
Incl/Excl criteria	X											
Vital signs	X	X	X	X	X	X	X	X	X	X	X	
Physical exam.	X	X	X	X	X	X	X	X	X	X	X	
Conc. Med.	X	X	X	X	X	X	X	X	X	X	X	X
eGFR ³	X	X	X	X	X	X	X	X	X	X	X	
Plasma Oxalate	X	X	X	X	X	X	X	X	X	X	X	
Stone events ⁴	X	X	X	X	X	X	X	X	X	X	X	X
Echocard. ⁵	X			X			X		X		X	
Ultrasound	X						X				X	
Safety Labs ⁶	X	X	X	X	X	X	X	X	X	X	X	
Stool	X			X			X		X		X	X
24-hour urine	X		X		X		X		X		X	
Quality of Life	X			X			X		X		X	
Pregnancy test ⁷	X										X	
Review Adverse events	X	X	X	X	X	X	X	X	X	X	X	X
Drug dispense/ Accountability	X	X	X	X	X	X	X	X	X	X	X	

¹ Month 0 (Visit 0; reference time point) will be the same as the last visit (Week 52) in ePHex. For echocardiography of the heart and ultrasound of the kidneys, week 48 measurements in ePHex are considered Month 0. If there is no seamless transition (delay >1 month) from ePHex, a new clinic visit 0 (Month 0) will take place with applicable measurements prior to first dose of open label Oxabact[®] and further assessments should follow according to schedule.

² Visit window during treatment period +/- 7 days. In the case of an acute kidney injury occurring close to a scheduled visit, the visit will be rescheduled to ensure that the AKI does not adversely affect values (especially for eGFR). The days on which each visit should occur are detailed in Table 6 of the protocol.

³ As determined by the Schwartz equation for children (age below 18), and CKD-EPI equation for adults (age 18 or above) based on serum creatinine.

⁴ Kidney stone events and related symptoms will be captured at every visit, including events in between visits.

⁵ Echocardiography to be done within +/- 2 weeks of the clinic visit at months 6, 12 and 18. If the images fail quality criteria, the examination will be repeated within 4 weeks.

⁶ Safety Labs will include blood and urine sampling.

⁷ If applicable.

⁸ A post-treatment safety follow-up will be performed as a telephone call (the safety follow-up period will cover a duration of four weeks and the telephone call will be made maximum 3 working days after the safety follow-up period).

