grade 0: no echogenicity

grade 1: mild echogenicity around medullary pyramid borders

grade 2: moderate echogenicity around and inside pyramids

grade 3: severe echogenicity of entire pyramids

Grades and shifts will be summarized for left and right kidney separately. In addition, shifts will be classified (and presented) following the addendum referred to in section 11.1. Shift tables will be presented as a crosstabulation comparing baseline and 12/24 months values.

Stool

Data collected for *O.formigenes* in stool (as genotype 1 and genotype 2) will only have measurable values if above the Limit of Detection (LOD). Values below the LOD will be replaced for calculation purposes in descriptive statistics, plots and statistical analyses (see section 11.1). The proposed analyses will only be performed if there is a limited amount (<15%) of data below LOD present on-treatment. The values will be presented as '< LOD' in the listings.

Note that in case of a provided actual value lower than the LOD, it will be presented and used as is and not imputed.

Based on previous studies, it is expected that the number of subjects positive for genotype 2 at screening/baseline and throughout the study will be very low. Therefore, in case genotype 1 or 2 is not detectable in the majority of data (see above), the analysis for that genotype will not be performed and data for that genotype will then be limited to a listing. All descriptive statistics and plots will be done separately on number of *O. formigenes* genotype 1 and 2 respectively, if applicable.

Descriptive statistics will be used to present the observed and change from baseline values per treatment group and overall over time, using two baselines. Change in number of *O. formigenes* stool will be based on number of *O. formigenes* at month 24 compared to baseline in the O - O group versus the P - O group. The measurement at month 12 will be used as supportive data.

Analyses on the total number of *O. formigenes* (i.e. the sum of genotype 1 and genotype 2) may be done as post-hoc analyses, and this depends upon the number of values <LOD.

Quality of Life questionnaires

Quality of life scoring is assessed with the questionnaires SF36V2 (for adults ≥ 18 years) or CHQ/PF50 (for children ≥ 5 years). For children younger than 5 years of age, it is likely that no information from the questionnaire is available, and data will remain missing.

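### The SAP gives no rule for deriving an ultrasound stone event and combines left and right counts, so a stone lost from one kidney can hide a new stone in the other

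*SAP*

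**What the plan says.** The ultrasound component of the endpoint is defined in two places. SAP 6.2 lists "Increase in number of stones assessed by ultrasound", and protocol 10.2 states: "An increase in number of kidney stones as seen in a kidney ultrasound would also be classified as a stone event". Neither says whether the increase is per kidney or per subject.

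SAP 7.6.2, which should turn this into an analysis, words the component as "or number of stones assessed by Ultrasound (US") and so leaves out the idea of an increase. It then says that, where applicable, "stones left and right will be combined into one overall kidney stone number for summary tables and analysis". Its incidence rate uses "Numerator: the total number of kidney stone occurrences during treatment (first to last dose date"), with no rule for converting ultrasound counts into occurrences. Reference scan, kidney level, order of summing and comparing, and number of events per increase are all unstated. Programming detail is deferred to Addendum 1 (SAP 11.1), which is not among the documents.

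On timing, protocol 6.2 says: "Ultrasound of the kidney will be done two times (months 12 and 24"). For ultrasound, the SAP 2.5 flow chart says that "week 48 measurements in ePHex are considered Month 0". For nephrocalcinosis, read from the same scans, SAP 7.6.3 says: "Grades and shifts will be summarized for left and right kidney separately".

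**The concern.** An increase in stones is meant to show new stone formation. A left-plus-right total shows only the net change for the subject. If one kidney gains a stone and the other loses one between scans, the total does not move and no event is recorded, although a stone formed.

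The combined number is the only ultrasound stone quantity that the SAP names for analysis. It would therefore feed the ultrasound versions of the incidence rate, rate difference and rate ratio with confidence intervals (SAP 7.6.2, Table 14.2.30) and, if sample size allows, the Poisson or negative binomial model (Table 14.2.33). The under-count grows with stone loss. Protocol 4.5.1 hypothesises that treatment dissolves oxalate deposits and cites stone dissolution in vivo, so loss is a process the sponsor expects.

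**Working it through.** No figure in the documents depends on this rule, so there is none to reproduce. The check compares two ways of deriving the event from left (L) and right (R) counts at consecutive scans 0 and 1.

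- Rule A (combined): event if L1 + R1 > L0 + R0.
- Rule B (per kidney): event if L1 > L0 or R1 > R0. The event count is max(0, L1 − L0) + max(0, R1 − R0).

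**Examples**

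| L0, R0 | L1, R1 | Change in total | Count, rule A | Count, rule B |
|---|---|---|---|---|
| 2, 1 | 1, 2 | 0 | 0 | 1 |
| 2, 2 | 1, 4 | +1 | 1 | 2 |
| 2, 2 | 2, 3 | +1 | 1 | 1 |

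Of the 25 left/right pairs of net change from −2 to +2, 16 have an increase in at least one kidney. Six of those 16 have no increase in the total: (−1, +1), (−2, +1), (−2, +2) and their mirror images. This counts patterns and is not a probability.

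**Interval length.** Month 0 is the ePHex week 48 scan, and later scans are at months 12 and 24. With a seamless transfer the first interval is about 13 months (4 weeks plus 12 months) and the second 12 months. Both gain and loss can occur within one interval.

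**Size under assumed rates.** Suppose stones form at rate a and are lost at rate b per kidney per interval, as independent Poisson counts. The net change in one kidney is Skellam(a, b). With p = P(Skellam(a, b) > 0):

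- P(increase in at least one kidney) = 1 − (1 − p)²
- P(increase in total) = P(Skellam(2a, 2b) > 0)
- share missed = 1 − (second ÷ first)

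| a | b | p | At least one kidney | Total | Share missed |
|---|---|---|---|---|---|
| 0.1 | 0.1 | 0.0865 | 0.1656 | 0.1513 | 9% |
| 0.25 | 0.25 | 0.1775 | 0.3235 | 0.2671 | 17% |
| 0.5 | 0.5 | 0.2671 | 0.4629 | 0.3457 | 25% |
| 0.25 | 0.5 | 0.1424 | 0.2645 | 0.1807 | 32% |

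**A simpler model gives a similar range.** Let each kidney independently change by +1 with probability g and by −1 with probability l. The share missed is 2gl ÷ [1 − (1 − g)²] = 2l ÷ (2 − g). For g = 0.2, l = 0.1 this is 0.2 ÷ 1.8 = 11.1%. For g = 0.3, l = 0.2 it is 0.4 ÷ 1.7 = 23.5%. For g = 0.4, l = 0.3 it is 0.6 ÷ 1.6 = 37.5%. With l = 0 nothing is missed.

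**What the per-kidney rule still misses.** At a = b = 0.25, the probability that at least one stone forms is 1 − exp(−0.5) = 39.3%. The per-kidney rule flags 32.3% and the total 26.7%. Rule B recovers 5.6 points and leaves 7.0 undetected, because gain and loss within one kidney also cancel.

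**Effect of more loss at fixed formation.** With a at 0.25 and b doubled from 0.25 to 0.5, the total's event proportion falls from 26.7% to 18.1% (ratio 0.68). The per-kidney proportion falls from 32.3% to 26.4% (ratio 0.82). True formation is unchanged at 39.3%. Both rules respond to loss, the combined one more strongly.

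**The case against.** The strongest reply is that the SAP does not prescribe the faulty order. It says the sides are combined where applicable, and increases found per kidney and then added would also fit that sentence. Addendum 1 may settle the matter. This stands: a reader might infer that the SAP orders the counts to be summed before an increase is sought, but the text does not say so. What remains is that the SAP states no derivation at all, and an endpoint definition belongs in the SAP itself.

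Second, neither document defines the event per kidney, so a net increase for the subject is compatible with the protocol. That also stands. Events are missed only relative to a per-kidney definition. The nephrocalcinosis comparison is weak support, since an ordinal grade cannot sensibly be summed and a count can.

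Third, a stone that was passed or removed is a stone event in its own right and can appear in the AE-based table. That holds if it was reported. The ultrasound table would still omit the new stone, and a stone that dissolved silently would appear in neither.

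Fourth, a reader might infer that the rule biases the comparison of the two groups in the drug's favour. The documents do not support this. Both O-O and P-O take Oxabact throughout the period analysed, and nothing shows that stone loss differs between them.

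Finally, the consequence is limited. Some 18 subjects have two on-treatment scans each, no formal testing is planned, and individual ultrasound data are listed. Opposite changes could be recovered from that listing if it shows the sides.

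**Conclusion.** The point holds as a gap in specification with a foreseeable consequence. SAP 7.6.2 drops the word that defines the ultrasound event, gives no derivation, and names only a combined count for analysis. If the increase is judged on that count, opposite changes in the two kidneys cancel and new stones are under-counted.

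The 9% to 32% range rests on assumed formation and loss rates, Poisson counts and independence between kidneys. It is a share of the subject-intervals that a per-kidney rule would flag, not of all stones formed. Without loss there is no under-count.

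Power and type I error are unaffected because the analysis is descriptive. The weight is modest: worth correcting because it is cheap, but not a demonstrated bias between O-O and P-O.

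**What to change.** Write the derivation into SAP 7.6.2:

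- Restore the word increase, in line with SAP 6.2 and protocol 10.2.
- For each scan interval, define ultrasound stone events as the sum over the two kidneys of max(0, count at this scan − count at the previous scan).
- Take the ePHex week 48 scan as the first reference, or the new Visit 0 scan where the transition was delayed.
- Keep the combined left-plus-right count as descriptive stone burden, and report the net increase in it as a sensitivity summary.

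Do not add recorded passages and removals back into the ultrasound count. They are already captured through the AE route. Adding them would also turn a fall from 3 to 2 stones with one passage into a new stone, and would need the side of each passage, which the documents do not show is recorded. They should stay in the AE-based table.

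The cost is one SAP paragraph and a small programming change; the SAP's instruction to combine the sides implies that ultrasound counts by side exist. Two drawbacks should be acknowledged: gain and loss within one kidney still cancel, and a per-kidney rule picks up slightly more scan-to-scan counting error.
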